11.5 Contractual Requirements

A contractual agreement will be signed between the CRO/Sponsor and each Investigator/Institution. This document will contain supplementary information, including financial terms, confidentiality, the clinical study schedule, third party responsibility, and publication rights.

11.6 Data Collection and Archiving

11.6.1 Data Collection

The Investigator must maintain all required records for all subjects. Data for this clinical study will be recorded in the subject's source documents and in the eCRFs provided by the Sponsor. All data should be recorded in the eCRFs completely and promptly.

11.6.2 Source Documentation

The Investigator must keep accurate separate records (other than the eCRFs) of all subject visits, being sure to include all pertinent clinical study-related information. A statement should be made indicating that the subjects have been included in this clinical study and have provided signed written Informed Consent. All AEs must be thoroughly documented.

Results of any diagnostic tests conducted during the clinical study should also be included in the source documentation.

11.6.3 Archives

All pertinent data, samples, photographs, correspondence, and reports, the original or amended clinical study protocol, and all other material relating to the clinical study will be maintained securely in Sponsor/CRO/Investigator/Institution archives for the legally required duration for archiving.

The Investigator/Institution should maintain the essential clinical study documents as specified in Section 8 of ICH-GCP, and according to the applicable regulatory requirements.

The Investigator/Institution should take measures to prevent accidental or premature destruction of these documents.

If the Principal Investigator retires, relocates, or withdraws from the responsibility of keeping the clinical study records for any other reasons, custody must be transferred to a person who will accept the responsibility. The Sponsor/CRO must be notified in writing of the name and address of the new custodian.

11.7 Insurance

A certificate attesting Third Party coverage of CRO/Sponsor will be provided upon request.

11.8 Publication Policy

The Institution/PI's and the Sponsor's obligations regarding intellectual property rights, confidentiality, and publications are described in detail in the CTA.

The aim is to submit the results of this study for publication in a public database (e.g., www.ClinicalTrials.gov) and to a medical journal for publication of the results. Everyone who is to be listed as an author of the results of this multicenter study shall have made a substantial, direct, intellectual contribution to the work. Authorship will be based on (1) substantial contributions to the conception or design of the work; or the acquisition, analysis, or interpretation of data for the work; and (2) drafting the work or revising it critically for important intellectual content; and (3) final approval of the version to be published; and (4) agreement to be accountable for all aspects of the work in ensuring that questions related to the accuracy or integrity of any part of the work are appropriately investigated and resolved.^a Conditions 1, 2, 3, and 4 must all be met in order to be designated as author. Those who do not meet all four criteria will be acknowledged. Among the authors that fulfil the above-mentioned criteria, one author will be appointed by the Sponsor to take primary responsibility for the overall work as primary author.

Defining the role of authors and contributors, compiled by the International Committee of Medical Journal Editors (ICMJE) (http://www.icmje.org).

Г		Title	Dec id
	GALDERMA	43QM1903 Clinical Study Protocol - QM1114 - LTS for LCL/GL	MA-40372

12.1 Protocol Version 4.0 to Version 5.0

[figure not shown]
Section in the clinical study protocol	Rational for changes	Description of changes
Schedule of assessments	Collection of neutralizing antibody blood sample before re-treatment and at 4 weeks after re-treatment	Blood sample for neutralizing antibody testing added at week 12, 16, 20, 24, 28, 32, 36, 40, and 44. Footnote 11 added ("Blood sample for serum antibody testing if subjects are eligible for re-treatment: before each re-treatment and 4 weeks after each re-treatment").
Section 7.2.4 (neutralizing antibody testing)	Collection of neutralizing antibody blood sample before re-treatment and at 4 weeks after re-treatment	"before any re-treatment, 4 weeks after re-treatment" added.
Section 8.1.4 (description of study visits)	Collection of neutralizing antibody blood sample before re-treatment and at 4 weeks after re-treatment	"Collect blood sample for neutralizing antibody testing prior to re-treatment" and "ONLY for re-treated subjects: collect blood sample for neutralizing antibody testing 4 weeks after each re-treatment" added for week 12, 16, 20, 24, 28, 32, 36 and 40.
Section 8.1.5 (description of study visits)	Collection of neutralizing antibody blood sample before re-treatment and at 4 weeks after re-treatment	"ONLY Week 44 visit for subjects retreated at Week 40: collect blood sample for neutralizing antibody testing" added for week 44.

14. APPENDICES

Appendix 1 Validated Investigator 4-point Photographic Scale of Glabellar Line Severity (GL-ILA)

[figure not shown]

43QM1903 Clinical Study Protocol - QM1114 - LTS for LCL/GL

MA-40372

Doe id

Effective date: 2020-08-26 19:44

Doe id

MA-40372

Validated Investigator 4-point Photographic Scale of Lateral Canthal Line Appendix 2 Severity (LCL-ILA)

Lateral Canthal Line Investigator Live Assessment (LCL-ILA) Relaxed

O None Smooth skin, no lines that are

1 Mild Lines that are noticeable but

2 Moderate Lines that are immediately noticeable and pronounced. 3 Severe Lines that are immediately

43QM1903 Clinical Study Protocol - QM1114 - LTS for LCL/GL

Doe id

MA-40372

Lateral Canthal Line Investigator Live Assessment (LCL-ILA) Dynamic

0 None

Smooth skin, no lines that are immediately noticeable.

1 Mild

Lines that are noticeable but not pronounced.

2 Moderate

Lines that are immediately noticeable and pronounced.

[figure not shown]
3 Severe

[figure not shown]
Lines that are immediately noticeable and extremely pronounced.

Doc id

-26 19:44

[figure not shown]

-40372

[figure not shown]
Doc id

8-26 19:44

[figure not shown]
Doe id

MA-40372

Doc id

MA-40372

	Title 42OM1902 Clinical Study Protocol OM1114 - LTS for LCL/CL	Doc id
♣ GALDERMA	43QM1903 Clinical Study Protocol - QM1114 - LTS for LCL/GL	MA-40372

Appendix 5 Focused Physical Examination Form Example			
Not done Provide details	s:		
General Health Assessment: Complete at Screening, Baseline (prior to treatment), Days 7 and 14 after each treatment, and Week 52/ET Question the subject about their general health (general wellbeing/ bodily functions, e.g., arms, legs, stomach/ bladder/ bowel, also refer to the list of Adverse Events Potentially Suggestive of Distant Spread of Toxin (Appendix 6). Abnormalities noted pre-injection should be recorded as medical history and Investigator should confirm if any abnormalities affect subject eligibility. Abnormalities noted post-injection should be assessed for clinical significance and recorded as AEs when appropriate.			
Next, proceed to the Focused Physic	cal Examinat	tion (Part 1 and 2) as indicated below.	
52/ET		ior to treatment), Days 7 and 14 after each treatment and Week ee, head, and neck recording abnormalities.	
Part 1 Examination	Normal	Abnormal* (provide details)	
Eyelid position			
Eyebrow position			
Vision abnormalities (not refractive errors)			
Throat function (e.g., swallowing/drink water)			
Ability to talk and chew			
Ability to stick out and move tongue			
Ability to lift shoulders			
* Abnormal findings at the screening and baseline visit, noted pre-injection, should be recorded as medical history and the Investigator should confirm if any abnormalities affect subject eligibility. Abnormalities noted after study treatment should be documented as AEs.			
Investigator Signature		Date	

	Title	Dec id
♣ GALDERMA	43QM1903 Clinical Study Protocol - QM1114 - LTS for LCL/GL	MA-40372

DADE A Complete of Daniel Control of Control			
PART 2: Complete at Days 7 and 14 after each	ch treatm	ent and Week 52/ET	
Not done Provide details:			
Local Spread of Toxin Effect refers to medial part of temporalis, zygomaticus Remote Spread of Toxin Effect refers to medial part of temporalis, zygomaticus Remote Spread of Toxin Effect refers to effect can only be attributed to the toxi	al or remore effects in a minor, zy to effects in and there in ficant (i.e.	areas adjacent to the treatment area (e.g., lower frontalis, gomaticus major, superior and inferior tarsal muscle). n other body parts, not adjacent to the treatment area, when the is no other medically sound cause. e., would affect subject safety, confound the study data, or	
		is (Appendix 6) while doing clinical evaluations based on examination will then be performed as appropriate. If yes,	
Part 2 Examination	No	Yes* (provide details)	
Targeted Physical Examination of Face and Neck to Evaluate Local Spread of Toxin Effect • Local spread of toxin effect event(s) observed?			
General Physical Examination to Evaluate the Remote Spread of Toxin Effect Remote spread of toxin effect event(s) observed?			
* Abnormalities should be documented as A	E,		
Additional comments for Focused Physical E	xam:		
Investigator Signature		Date	

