Appendix 5 Focused Physical Examination Form Example83
Appendix 6 Adverse Events Potentially Suggestive of Remote Spread of Toxin85
SIGNED AGREEMENT OF THE CLINICAL STUDY PROTOCOL86

List of Tables

Table 1	Schedule of Assessments	16
Table 2	Description and Usage of the Study Product	37
	List of Figures	
Figure 1	Study Flow Chart	15
Figure 2	Injection Sites for Treating Glabellar Lines	39
Figure 3	Injection Sites for Treating LCL Option 1	40
Figure 4	Injection Sites for Treating LCL Option 2	40

SYNOPSIS				
Clinical Study Title: A Multicenter, Open-Label Study to Evaluate the Safety of QM1114-DP for the Long-term				
	Treatment of Moderate to Severe Glabellar Lines and Lateral Canthal Lines (READY - 4) Short Title: QM1114-DP Long-term Treatment of GL and LCL			
	satirent of GL and LGL			
Clinical Study Population:	Male and female subjects, 18 years of age and older, with moderate to severe glabellar lines (GL) at maximum frown and moderate to severe bilateral lateral canthal lines (LCL) at maximum smile.			
Clinical Study Design:	This is a phase 3, multicenter, open-label study to evaluate the safety of QM1114-DP for the long-term treatment of moderate to severe GL and LCL.			
	Eligible subjects will receive up to 4 treatments of QM1114-DP in the GL and/or LCL and will be monitored for safety and efficacy over a period of up to 52 weeks.			
	The first treatment will be administered at Day 0 (Baseline). Re-treatments can be administered at any of the follow-up visits from Week 12 to Week 40, provided that the subject is eligible for re-treatment and there has been at least 12 weeks since the last treatment. Follow-up visits for treated subjects are conducted at Day 7 and Day 14 after each treatment. Follow-up visits, i.e. not treatment dependent, are scheduled at Week 4, 8, 12, 16, 20, 24, 28, 32, 36, 40, 44, 48 and 52.			
	To ensure a sufficient amount of long-term safety data is included in the database per ICH E1 guidelines, approximately 900 subjects will be enrolled; all subjects will be followed for at least 24 weeks and at least 300 subjects will be followed up to 52 weeks. The study may be stopped when at least 300 subjects have completed the Week 52 study visit.			
Target Indication:	This study is designed to evaluate the safety of QM1114-DP for the long- term treatment of moderate to severe GL and LCL.			
Total Number of Subjects (Planned):	Approximately 900 subjects will be enrolled.			

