2.1.1 Primary Objectives and Endpoints

The primary objective of this study is to evaluate the safety of repeated injections of QM1114-DP for the treatment of moderate to severe GL and LCL.

Primary endpoints include:

- Incidence and severity of treatment emergent AEs (TEAEs)
- Focused physical examination (FPE) findings

[figure not shown]

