7.2.5.1.7 Relationship to the Study Product and/or Clinical Study Procedure

The Investigator is to determine whether there is a reasonable causal relationship between the occurrence of the AE and exposure to the study product and/or clinical study procedure.

Medical judgment should be used to determine the relationship, considering all relevant factors including the pattern of reaction, temporal relationships, relevant medical history, and confounding factors such as co-medication or concurrent diseases.

The expression "reasonable causal relationship" is meant to convey in general that there are facts or arguments to suggest a causal relationship (ICH E2A, Section IIIA 1).

The relationship assessment for an AE is to be completed using the following definitions as a guideline:

Reasonable Possibility: According to the reporting Investigator, there is a reasonable possibility (i.e., suggestive evidence or arguments) that there is a causal relationship irrespective of the dose administered between:

- The study product and the AE.
- The clinical study protocol procedure (e.g., bruising or marks from blood draws, injection related trauma, etc.) and the AE.

A two-point scale (Yes or No response) shall be used for the causality assessment. The Investigator shall be asked to indicate a response to each of the following questions in the eCRF:

- "Do you consider that there is a reasonable possibility that the event may have been caused by the study product?", and
- "Do you consider that there is a reasonable possibility that the event may have been caused by the study product injection procedure?"

If any of these questions is answered Yes, the AE is considered related.

No Reasonable Possibility: No suggestive evidence or arguments can be identified regarding a causal relationship between the study product or the clinical study protocol procedure and the AE.

	Title	Doc id
♣ GALDERMA	43QM1903 Clinical Study Protocol - QM1114 - LTS for LCL/GL	MA-40372

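### The examination form counts remote spread of toxin only when no other cause is medically sound, a stricter test than the protocol's own causality rule, so the labelled count can only be equal or lower

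*Protocol*

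**What the plan says.** Section 2.1.1 lists "Focused physical examination (FPE) findings" as a primary endpoint beside treatment-emergent adverse events. Section 7.2.1 refers to Appendix 5 for the details of the examination.

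Part 2 of the Appendix 5 form is completed at Days 7 and 14 after each treatment and at Week 52 or early termination. It has a Yes/No item: "Remote spread of toxin effect event(s) observed". The form defines remote spread as effects in body parts not adjacent to the treated area, when the "effect can only be attributed to the toxi" (the final word is broken in the extracted text) and there "is no other medically sound cause". The legible definition of local spread is anatomical and carries no such condition.

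Elsewhere the threshold is lower:

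- Section 7.2.5.1.7 treats an event as related when "there is a reasonable possibility (i.e., suggestive evidence or arguments" point to a causal link. The investigator answers "Do you consider that there is a reasonable possibility that the event may have been caused by the study product" and a parallel question about the injection procedure. The rule is: "If any of these questions is answered Yes, the AE is considered related".
- The list to be consulted is titled "Appendix 6 Adverse Events Potentially Suggestive of Remote Spread of Toxin".
- Section 1.3 says subjects will be queried for any potential signs and symptoms of local and distant spread.

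Section 9.1.4 summarizes physical examination results by visit and cycle.

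**The concern.** The item is worded as an observation but defined as a diagnosis of exclusion. A subject with new dysphagia or limb weakness, suggestive timing and a plausible competing illness would be a related adverse event under section 7.2.5.1.7 and a No on Part 2. Nothing in the protocol reconciles the two answers.

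The decision falls to an investigator in an open-label study, at fixed visits when a work-up to exclude other causes may be unfinished. Section 7.2.5.1.1 says that remote spread affecting swallowing and breathing can be life threatening. A low or zero Part 2 count could be quoted as the trial's remote-spread result when part of it reflects the definition.

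**Working it through.** The protocol gives no expected rate of remote spread and no statistical basis for the sample size (section 9.2), and all analysis is descriptive (section 9.1.6). There is no figure to reproduce, so the check is a comparison of definitions, with one illustration.

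**Step 1: compare the two tests for one event in a non-adjacent body part.**

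| Situation | Section 7.2.5.1.7 (product question) | Appendix 5, Part 2 |
|---|---|---|
| Toxin is the only sound explanation | Related | Yes |
| Suggestive of toxin, another sound cause also present | Can be related; confounders are weighed | No |
| No suggestive evidence of a toxin effect | Not related | No |

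The second row is where the documents give discordant answers.

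**Step 2: direction.** Let R be the non-adjacent events with a reasonable possibility of relation to the product, and E those attributable only to the toxin. Every event in E is also in R, so the count of E is at most the count of R. The direction is fixed by the wording. The gap is the number of second-row events, which the documents do not give.

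**Step 3: what a zero would mean.** The one-sided 95% upper bound for zero events in n subjects is 1 − 0.05^(1/n).

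- n = 900 (planned enrolment): 1 − 0.05^(1/900) = 0.33%.
- n = 300 (minimum planned to reach Week 52): 1 − 0.05^(1/300) = 0.99%.

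Taken from Part 2, either bound describes only the exclusively attributable subset E.

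**Step 4: illustration only.** Assume a true per-subject rate p of events meeting the reasonable-possibility standard, and a share s of them that also meet the exclusive test. Neither figure is in the protocol. Expected count = n·p·s and P(zero recorded) = (1 − p·s)^n, with n = 900.

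| p | s | Expected count | P(zero) |
|---|---|---|---|
| 0.5% | 1 | 4.5 | 0.011 |
| 0.5% | 0.5 | 2.25 | 0.105 |
| 0.5% | 0.2 | 0.9 | 0.406 |
| 0.5% | 0.1 | 0.45 | 0.638 |
| 0.2% | 1 | 1.8 | 0.165 |
| 0.2% | 0.2 | 0.36 | 0.698 |
| 1% | 0.2 | 1.8 | 0.165 |

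At p = 0.5%, moving from s = 1 to s = 0.2 raises the chance of a zero from about 1% to about 41%. The table shows how the result depends on s. It does not estimate s.

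**The case against.** The strongest reply is that nothing is lost.

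- **Part 1 of the same form** records vision, swallowing, talking and chewing, tongue movement and shoulder lift as normal or abnormal, with no attribution test. The general health questions cover arms, legs, stomach, bladder and bowel with reference to Appendix 6.
- **Adverse event capture.** Section 7.2.1 sends post-injection abnormalities to the adverse event form. Section 7.2.5.2.1 records events whether related or not. Section 9.1.4 tabulates them by system organ class and preferred term, with a separate table of related events.

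This stands. A reader might infer that the primary endpoint misses suggestive signs; the documents do not support that. What the reply leaves untouched is the count that carries the remote-spread label. The adverse event tables do not correct it; they place a second, possibly different answer beside it. Capture outside the head and neck is also slightly looser: the form's general health section records abnormalities as adverse events when appropriate, after a judgement of clinical significance.

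A second reply is that a syndrome definition and a causality rule serve different purposes, so a related event that fails a strict case definition is no strict contradiction. That is fair. But the form gives the strict definition alone, under a question phrased as an observation.

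Third, Appendix 5 is headed an example, its Part 2 text is broken in extraction, and Appendix 6 is not in the text at hand. Qualifying instructions cannot be excluded, though the two decisive phrases are legible.

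Finally, the analysis plan may well group the Appendix 6 terms. The absence of such a table from section 9.1.4 is therefore no part of this point. A grouped table would still leave the form's definition as it is.

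**Conclusion.** The point holds for the Part 2 remote-spread item. Its definition is stricter than the protocol's causality standard and than the suggestive-event list the form cites. The labelled count within the primary FPE endpoint can therefore only equal or fall below the count under that standard. The size of any shortfall cannot be derived from the documents; the figures in step 4 rest on assumed p and s.

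A reader might go further and infer that a zero is built in, or that investigators must almost always answer No because some other cause is always conceivable. The text does not support either. The condition is a medically sound alternative in the actual subject, not any imaginable one, and the definition lowers the count by an unknown amount, possibly none.

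The consequence is limited to the labelled count and to any statement, based on it, that no remote spread was observed. That is worth correcting because of the risk concerned and because the change is cheap.

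**What to change.** Reconcile Appendix 5 Part 2 with section 7.2.5.1.7 and Appendix 6:

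1. Reword the Part 2 item to ask whether any new or worsened sign or symptom potentially suggestive of remote spread (Appendix 6) was observed, with no attribution condition. The wording must change along with the definition: answering Yes to observed remote spread for any listed symptom would mislabel unrelated illness.
2. Take attribution from the two existing reasonable-possibility questions on the adverse event form.
3. Report two counts: all suggestive events, and those with a reasonable possibility of relation.
4. If the exclusive-cause category is kept, report it only as an additional subset.

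The cost is one definition, the matching form text and one extra table. The broader count will include some events from other causes and will overlap with Part 1; the second count separates out those with a reasonable possibility of relation. No clinical management changes.
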